## 6.0 STUDY DESIGN AND DESCRIPTION

### 6.1 Study Design

This phase 1b/2a, multicenter, randomized, double-blind, placebo-controlled, parallel-group, dose-escalation study with an open-label part is designed to examine the safety, tolerability, PK, and PD of TAK-935 as adjunctive therapy in adult subjects with a diagnosis of developmental and/or epileptic encephalopathies. This study will be conducted at approximately 11 sites in North America with experience in conducting clinical studies in patients with rare epilepsies.

Adult subjects (aged  $\geq 18$  and  $\leq 65$  years) with a diagnosis of developmental and/or epileptic encephalopathies demonstrating bilateral motor seizures (ie, drop seizures, tonic-clonic, tonic, bilateral clonic, atonic, myoclonic-atonic, myoclonic-tonic-clonic, focal seizures with bilateral hyperkinetic motor features) (average of  $\geq 2$  per month during the past 3 months) based on the investigator's assessment will be enrolled. The study will screen a sufficient number of subjects to ensure approximately 20 randomized subjects.

At the Screening Visit (Visit 1), informed consent and/or assent (if applicable) is obtained from the subjects and/or subjects' legally acceptable representative. Subjects will then undergo screening procedures to assess study eligibility in accordance with the study entry criteria (see [Appendix A](#) and Sections 7.1 and 7.2). CCI

The 4-week Baseline Period CCI can begin as soon as informed consent has been signed. At the end of the 4-week Baseline Period and after confirmation of eligibility, subjects will return to the clinic on Day 1 in Part 1 (Visit 2) for randomization. If a subject does not meet the eligibility criteria during the Screening/Baseline Period, the subject will be discontinued from the study (screen failure).

The study will consist of 2 parts:

- Part 1 is a randomized double-blind part consisting of 3 periods: a screening/baseline period (4-6 weeks), titration period (20 days), and maintenance period (10 days). The target final dose of 300 mg BID will be reached after a 20-day titration period.
- Part 2 is an open-label continuation part consisting of 4 periods: a titration period (10 days), maintenance period (44 days), de-escalation period (3-6 days) and follow-up period (30 days).

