On Day 31 (Visit 5), PK, PD, AED, and PGx (if collected on Day 1) blood samples will be collected before the morning dose of study drug and seizure data will also be collected. On Day 41 (Visit 6), PK, PD, and AED blood samples will be collected before the morning dose of study drug and seizure data will also be collected.

On Day 85 (Visit 7), subjects will return to the clinic for the Final Visit and enter the 3- or 6-day de-escalation phase. At this visit, PK, PD, and AED blood samples will be collected before the morning dose of study drug and seizure data will also be collected. Subjects will then enter the dose de-escalation phase and will be instructed to follow the applicable de-escalation dosing schedule outlined below:

- For subjects on 300 mg BID during the maintenance phase, the dose will be de-escalated to 200 mg BID for 3 days (Days 85-87) and subsequently to 100 mg BID for 3 days (Days 88-90).
- For subjects on 200 mg BID during the maintenance phase, the dose will be de-escalated to 100 mg BID for 3 days (Days 85-87).
- For subjects on 100 mg BID during the maintenance phase, there is no de-escalation and the dose is discontinued on Day 85.

Immediately after the last dose is the 30-day Follow-up Period comprised of a Follow-up Phone Call (Visit 8) on Day 91 and a Follow-up Visit (Visit 9) on Day 121. At the Follow-up Visit, subjects will return to the clinic for study procedures including PD and AED blood sample collection.

In Parts 1 and 2, subjects will be instructed to not take their morning dose of study drug or concomitant AEDs on the days of scheduled study visits to facilitate collection of the predose PK, PD, AED, and optional PGx blood samples. The morning dose of study drug and concomitant AEDs will be administered in the clinic on these study days after laboratory samples are collected. For subjects who are not able to come for the visit during the morning hours, they should be instructed to take their morning dose, as usual, and come to the study site during the afternoon hours, as feasible for the subject. While in the clinic, the site should attempt to obtain 2 PK samples, separated by 1-2 hours, if possible. Hours since the last dose of the study medication must be recorded in the eCRF upon collection of the PK sample(s).

[figure not shown]

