**CONFIDENTIAL**

morning hours, they should be instructed to take their morning dose, as usual, and come to the study site during the afternoon hours, as feasible for the subject. While in the clinic, the site should attempt to obtain 2 PK samples, separated by 1-2 hours, if possible. Hours since the last dose of the study medication must be recorded in the eCRF upon collection of the PK sample(s).

(o) Plasma samples for measurement of concomitant AED concentrations will be collected before the morning dose on Days 1, 11, 21, 31, 41, and 85; and at the Follow-up Visit (Day 121).

CCI

(q) One PGx blood sample for DNA isolation will be collected before the morning dose on Day 1.

(r) Two PGx blood samples for RNA isolation will be collected before the morning dose on Days 1 and 31.

(s) The dose of IP will be increased on Days 11 and 21 in Part 1 and on Day 41 in Part 2, provided there are no safety or tolerability concerns. Subjects' dose may be increased or decreased before Day 41 (Visit 6) based on clinical condition (ie, increasing seizures) and investigator judgment. At the end of Part 2, the dose of TAK-935 will be de-escalated before dosing is discontinued. See Section 6.1 for details.

(t) A dosing card will be provided to record daily AM and PM study drug administration throughout the study, including changes in dosing regimen (de-escalation) that may occur between visits and during the de-escalation period of the study.

(u) On in-clinic dosing days, after administration of study drug, appropriate mouth and/or hand checks will be performed to ensure that the dose is swallowed and noted in the source document. If a site visit is not possible during the morning hours, the subject should take their morning dose prior to attending the visit during the afternoon hours. The date and time of each dose will be recorded in the source documents and on the eCRFs.

(v) Collection of AEs will commence from the time informed consent is provided (Screening Visit) and continue until screen failure or the Follow-up Visit.

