#### 7.1.2 Definitions of Study Visit Windows

For each visit, a window will be defined; this window will establish a time interval around which data will be considered for the analysis of the scheduled visit pertaining to that window. The lower and upper bounds of each window are the approximate midpoints between the scheduled days for the current visit and its adjacent scheduled visits. The value used in analysis for by-visit

summaries is the value within the specified window that is closest to the scheduled study day. If two observations are equidistant from the scheduled visit date, the observation with a later date will be used. The visit windows and applicable study day ranges are presented below in [Table 7.a](#) and [Table 7.b](#). Cut-off days for inclusion in the window (number of days following the date of the last dose of open-label study drug) are provided.

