**Table 7.b Visit Analysis Windows for Part 2**

Visit	Scheduled Visit Day	Visit Window (Days)				
		Vital Signs, CCI, PK, C, Plasma Sample for AED, Concomitant Medications	CCI	ECG, Clinical Laboratory Tests	CCI, Serum/urine Pregnancy Test	Physical Exam, Neurological Exam
Baseline II		≤First Dose in Part 2	≤First Dose in Part 2	≤First Dose in Part 2	≤First Dose in Part 2	≤First Dose in Part 2
Visit 6	41	Day after First Dose in Part 2-53	Day after First Dose in Part 2-53			
Visit 7	85	54-Last Dose+7	54-Last Dose+7	Day after First Dose in Part 2-Last Dose+7	Day after First Dose in Part 2-Last Dose+7	Day after First Dose in Part 2-Last Dose+7

Note: Any value collected after the administration of first dose in Part 2 will be grouped under day after first dose in Part 2, except for PK, CCI and plasma sample for AED.

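### The Day 121 AED sample, the only one scheduled after TAK-935 has stopped, has no window in SAP Tables 7.a and 7.b, so the windowed by-visit summaries leave it out

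*Protocol*

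**What the plan says.** Protocol 6.1 divides Part 2 into four periods: "a titration period (10 days), maintenance period (44 days), de-escalation period (3-6 days) and follow-up period (30 days"). Of the clinic visit that ends follow-up it says: "At the Follow-up Visit, subjects will return to the clinic for study procedures including PD and AED blood sample collection". Appendix A footnote (o) places AED samples before the morning dose on Days 1, 11, 21, 31, 41 and 85, "and at the Follow-up Visit (Day 121"). The Appendix A grid marks both AED and PD at that visit.

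SAP 7.1.2 undertakes to give every visit a window, with bounds at roughly the midpoints between neighbouring scheduled visits. What enters by-visit "summaries is the value within the specified window that is closest to the scheduled study day". The first window column of Table 7.b names AED samples in its header: "Plasma Sample for AED, Concomitant Medications". Table 7.a has the same item. In both tables that column ends with Visit 7, running from Day 54 to seven days after the last dose, and neither table has a row for Visit 8 or Visit 9. The notes under both tables exempt AED samples from the first-dose-day rule, so the tables are meant to govern them.

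SAP 7.11.2 to 7.11.4 state a seven-day limit separately for the laboratory, vital sign and ECG tables. SAP 7.9.2, SAP 7.9.3, Tables 7.d and 7.e, and one item in the window headers are redacted.

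**The concern.** A cut at last dose + 7 days suits on-treatment safety tables. Applied to AED levels, it removes the one scheduled sample taken after washout. The secondary objective concerns TAK-935 pharmacokinetics in subjects on concomitant AEDs, so a change in AED level during treatment is a natural question. If a level shifts on TAK-935 and returns by Day 121, an interaction is the likelier explanation. If it shifts and does not return, drift or a change in background therapy becomes more plausible. For a subject randomized to TAK-935, the scheduled off-drug AED samples are Day 1 and Day 121. Without Day 121, the windowed summary has only the pre-drug value and cannot show whether a change reverses.

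**Working it through.** **Is the sample planned?** Yes. Footnote (o) gives seven AED sampling days. Protocol Table 9.a budgets 28 mL for AED at 4 mL per sample, and 7 x 4 = 28. The sample counts printed in that row (3 + 3) would give only 6 x 4 = 24, so the total includes Day 121.

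**Last dose day** (Protocol 6.1)
- 300 mg BID maintenance: "subsequently to 100 mg BID for 3 days (Days 88-90"), so Day 90.
- 200 mg BID: "the dose will be de-escalated to 100 mg BID for 3 days (Days 85-87"), so Day 87.
- 100 mg BID: "there is no de-escalation and the dose is discontinued on Day 85". This can be read as a last dose on Day 84 or Day 85; both are carried below.

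**Window close = last dose day + 7**, compared with Visit 9 at Day 121 ± 2 (Days 119 to 123):

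| Maintenance dose | Last dose | Window closes | Day 121 past close | Days 119-123 past close |
|---|---|---|---|---|
| 300 mg BID | 90 | 97 | 24 days | 22-26 days |
| 200 mg BID | 87 | 94 | 27 days | 25-29 days |
| 100 mg BID | 84 or 85 | 91 or 92 | 30 or 29 days | 27-32 days |

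**Most favourable case.** Visit 7 is two days late (Day 87) with six days of de-escalation, so the last dose is Day 92 and the window closes on Day 99. Visit 9 is two days early, on Day 119. The gap is 119 - 99 = 20 days.

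**Subject who stops after Part 1 from 300 mg BID.** The Final Visit is on Day 31 and de-escalation runs over Days 31-36, so last dose + 7 is Day 43. Follow-up is at about 36 + 30 = Day 66, which is 23 days past that cut and beyond the Visit 6 range (Days 37-53) of Table 7.a. The Visit 7 range would start on Day 54 and end on Day 43, so it is empty.

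**The SAP's own midpoint rule.** Midpoints of Days 11/21, 21/31 and 31/41 are 16, 26 and 36, as printed. For Days 41/85 the midpoint is 63 where the SAP prints 53, so the rule is not followed throughout. For Days 85/121 it is (85 + 121)/2 = 103. A Visit 9 window built by this rule would open at about Day 104 and contain Days 119-123.

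**The case against.** The strongest objection is that the sections that would settle the matter are blacked out. SAP 7.9.2, 7.9.3 and Tables 7.d and 7.e may list Day 121 as a nominal time point, and redacted text cannot be counted as absent. The visible PK counterpart, SAP Table 7.c, works by nominal time. One value per window also could not produce tables for samples drawn at predose, 1, 3 and 5 hours on Day 1. This has force for PD. It has less for AED, which is drawn once per scheduled visit and is named in the window column. If the redacted text does use Day 121, it still has to be reconciled with tables that give that visit no window.

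A reader might infer more than the documents support:
- That PD is excluded in the same way. This is likely, but the PD label in the header is redacted. PD also has a screening sample, so Day 1 is not its only pre-drug reference.
- That Day 121 holds the only post-drug data in the trial. Vital signs, the behavior checklist, the seizure diary and AEs also extend to Day 121, and TEAEs are counted to 30 days after the last dose. An early withdrawer's Final Visit sample could be off drug and still in window.
- That no other control for drift exists. The four planned placebo subjects have AED samples off TAK-935 on Days 1, 11, 21 and predose Day 31.
- That the samples are lost. Listings and the separate population PK/PD report (Protocol 13.1.4) do not depend on these windows.
- That the protocol states why the Day 121 AED sample is drawn. No visible text gives its purpose; the use described here is a statistical reading.

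AED levels are not among the primary or secondary endpoints. Twenty subjects on 1 to 4 AEDs, over 13 assays, average 20/13 = 1.5 to 80/13 = 6.2 subjects per assay if every AED taken is assayed. Follow-up summaries would be thin. That limits the importance of the point but does not justify leaving the visit without a rule.

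**Conclusion.** The point holds for AED. On the visible text, no on-schedule Day 121 AED sample falls in any SAP window. The gap is 22 to 32 days when Visit 7 is on schedule, and 20 days with the most favourable use of the visit windows. The loss is confined to windowed by-visit summaries. For PD it is probable but not shown. The conclusion assumes that the redacted sections do not override SAP 7.1.2.

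The arithmetic covers completers and subjects who leave after Part 1 from 300 mg BID. Early withdrawers differ. As printed, the Visit 3 to Visit 6 rows of Table 7.a are bounded by study day alone. A subject whose last dose is on or before Day 23 would have a 30-day follow-up sample by Day 53 (23 + 30), which could be counted as a Visit 6 or earlier value although it is off drug.

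This is a worthwhile correction to a non-primary analysis and does not threaten the trial's main conclusions.

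**What to change.** Add a row to Table 7.b labelled Visit 9 / Follow-up (off drug) for plasma AED, and for PD if it shares that column. It could open at about Day 104, by the midpoint rule, or at last dose + 8 days. Add an equivalent row for subjects who do not enter Part 2. The last-dose form suits them better, because a start at Day 104 would miss a follow-up at about Day 66. State that an off-drug sample goes to this row ahead of any row set by study day.

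Report the Visit 9 value, its change from Day 1, and its change from the last on-drug value as separate lines. Averaging Day 1 with Visit 9 into one off-drug reference is not advised: it assumes no drift, which is what the follow-up value helps to check.

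Reconcile the new row with SAP 7.9.2, 7.9.3 and Tables 7.d and 7.e. If exclusion is intended, say that Day 121 AED samples are listed only. Keep the last dose + 7 cut for the laboratory, vital sign and ECG tables.

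The cost is SAP wording, one table row with its Part 1 equivalent, and a few lines of output. No additional blood or data collection is needed.

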## 6.2 Justification for Study Design, Dose, and Endpoints

### 6.2.1 Study Design

This is a multicenter, randomized, double-blind, placebo-controlled, parallel-group, dose-escalation study with an open-label part to examine the safety, tolerability, PK and PD, and preliminary efficacy of TAK-935 as adjunctive therapy in the treatment of subjects with a diagnosis of developmental and/or epileptic encephalopathies demonstrating bilateral motor seizures (ie, drop seizures, tonic-clonic, tonic, bilateral clonic, atonic, myoclonic-atonic, myoclonic-tonic-clonic, focal seizures with bilateral hyperkinetic motor features) (average of  $\geq 2$  per month during the past 3 months) based on the investigator's assessment.

The safety, tolerability, PK, and CCI of TAK-935 after multiple-dose administration either orally or via G-Tube/PEG tube is first assessed (in Part 1), and then the longer-term safety, tolerability, and PK/PD of TAK-935 is assessed (in Part 2), with a seamless transition between Parts 1 and 2. The main goal of this study is to identify the safe and tolerable dose of TAK-935 to assess the efficacy of TAK-935 in subjects with developmental and/or epileptic encephalopathies.

### 6.2.2 Dose

#### 6.2.2.1 Dose Selection Rationale

In the current study, dose selection was mainly based on the safety and tolerability data from the single- and multiple-dose phase 1 studies in healthy subjects administered TAK-935 as an oral solution. The selection of BID doses was also supported by the PK/PD/enzyme occupancy (EO) modeling and simulations using available phase 1 data. In addition, nonclinical data from rodent epilepsy models were used to define efficacious doses.

The safety results from the phase 1 studies show that TAK 935 (up to a single dose of 1350 mg) is generally safe and well tolerated in healthy male and female subjects. TAK-935 has been evaluated at doses up to 600 mg once daily (QD) as well as 300 mg BID in healthy adult subjects in the MRD study. Multiple rising doses of TAK-935 up to 400 mg QD for 14 days without up-titration was generally safe and well tolerated in healthy subjects. When administered in a nontitrating fashion, AEs considered by the investigator to be nonserious were seen in individual subjects at 300 mg BID (mental confusion of mild intensity) and 600 mg QD (acute psychosis of severe intensity) dose levels. This TAK-935-2001 study will continue to investigate safety, tolerability, PK, and PD of TAK-935 by studying a dose range of 100 mg BID to 300 mg BID in an epilepsy adult patient population. In this study, a titration scheme will be used to ensure safety and tolerability before moving to higher doses.

In pentylenetetrazol (PTZ)-induced kindling in mice, TAK-935 at a dose of 1 mg/kg resulted in a statistically significant reduction in seizure counts. This dose also resulted in an approximately 60% reduction in mean brain 24HC levels, which translated to an average EO of approximately

65%. At higher doses, TAK-935 exerted stronger effects on generalized seizures. The 1 mg/kg dose was determined to be the minimum effective dose of TAK-935.

A selective PET ligand was developed and used to assess the CNS target engagement of TAK-935 in healthy adult subjects, and a preliminary PK/PD/EO model was developed. Firstly, an empirical PK model was developed to characterize complex and nonlinear PK data in healthy adult subjects from the SRD and MRD studies as well as the relative BA study comparing the exposure between oral dosing with solution and tablet formulations. Subsequently, the predicted TAK-935 plasma concentrations were modeled with PD (24HC and PET occupancy) data to assess target engagement. The relationship between TAK-935 plasma concentrations and the observed brain occupancy values was characterized by a sigmoidal maximum effect model using an effect-site compartment to account for the temporal lag observed between PK and PD measurements. The relationship between TAK-935 plasma concentrations and plasma 24HC levels was characterized by an inhibitory indirect response model. This PK/PD/EO model was used to select the doses for the current study. The model-based simulations were performed for both QD and BID dosing regimens with the same daily dose in adult subjects, and the BID regimen was selected over QD regimen due to its lower variability on the expected EO, PK, and PD parameters and a more sustained period during a dosing interval with EO above 65%.

#### 6.2.2.2 Dose Selection Procedures

The planned doses are based on predictions from the available PK/PD/EO model. A TAK-935 100 mg tablet, administered as 1, 2, or 3 tablets corresponding to the different dose levels, will be used for dosing in adult subjects.

The EO levels and planned TAK-935 doses are shown for each part of the study in [Table 6.a](#).

**Table 6.a Planned TAK-935 BID Doses and Associated Estimated EO Levels**

TAK-935 BID Dose (mg)	Average EO Level (%) (a)
300	85-95
200	80-90
100	70-80

(a) Average EO% at steady state during a dosing interval.

The investigator, in consultation with the sponsor, may decide to reduce the IP (TAK-935 or placebo) during Part 1 and TAK-935 during Part 2 dose at any time during the study, in the event of any safety or tolerability concerns. In Part 1, the planned starting dose of TAK-935 for adult subjects is 100 mg BID to achieve an average steady-state EO of approximately 70% to 80%. If well tolerated, this dose will be increased to 200 mg BID on Day 11 and subsequently to 300 mg BID on Day 21; the average steady-state EO at these doses are expected to be approximately 80% to 90% and 85% to 95%, respectively ([Table 6.a](#)).

In Part 2, the planned starting dose of TAK-935 for all subjects, including those who received placebo in Part 1, is 200 mg BID to be increased to 300 mg BID. The dose may be decreased at any time due to safety or tolerability concerns.

### 6.2.3 Endpoints

#### 6.2.3.1 Safety Endpoints

The safety-related endpoints of TEAEs, clinical laboratory test results, vital sign measurements, C-SSRS, and ECG parameters selected for this study are standard methods for assessing safety and tolerability in clinical studies. The ABC-C is a standard tool for measuring the severity of a range of problem behaviors commonly observed in individuals with intellectual and developmental disabilities.

#### 6.2.3.2 PK Endpoints

The secondary PK endpoints selected for this study,  $C_{max}$ ,  $AUC_{0-tau}$ ,  $C_{av,ss}$ , and  $C_{trough}$  are common PK parameters used to describe the steady-state exposure of a study drug following multiple doses in clinical studies. Additional population PK parameters will be included in the population PK model used to characterize the TAK-935 concentration-time profile and will be reported in the population PK report.

#### 6.2.3.3 CCI [REDACTED]

CCI [REDACTED]

#### 6.2.3.4 CCI [REDACTED]

CCI [REDACTED]

### **6.3 Premature Termination or Suspension of Study or Study Site**

#### **6.3.1 Criteria for Premature Termination or Suspension of the Study**

The study will be completed as planned unless 1 or more of the following criteria are satisfied that require temporary suspension or early termination of the study.

- New information or other evaluation regarding the safety or efficacy of the study drug that indicates a change in the known risk/benefit profile for TAK-935, such that the risk is no longer acceptable for subjects participating in the study.
- Significant violation of Good Clinical Practice (GCP) that compromises the ability to achieve the primary study objectives or compromises subject safety.

